Participants. Our approach will be to develop a human cohort derived from a study already nearing completion in Montreal (The Montreal Prematurity Study funded by the March of Dimes; PI: [name]). [name] is a collaborator on the MAVAN project, and Drs. [name] and [name] are collaborators on the Prematurity Study. The Prematurity study involves measures of psychosocial stress, nutrition, and family and community living conditions as predictors of gestational length, which is the outcome measure in this project. This project will recruit 5000 women at 13-15 weeks gestation, of which approximately 4000 have been recruited and will have given birth before the start of our project, leaving a population of 1200 potential subjects. Currently, 100 women each month are assessed at 24-26 weeks gestation. There is currently in place an infrastructure for follow-up of women from the Montreal Prematurity Study.

The cohort for the current MAVAN project will be derived from the same population used in the Prematurity Study. In essence the MAVAN Project will serve as a follow-up study derived from the Prematurity Study focusing on a substantially smaller population. The strategy for the MAVAN Project is to take advantage of the multivariate assessment of prenatal adversity in The Montreal Prematurity Study. We will follow infants born at normal weight (controls, n= 120; 3000-3500 g at birth) and low-

birth weight babies exhibiting evidence for intrauterine growth retardation (IUGR, n= 120; 2200-2750 g at birth). These groups are based on the recently published Canadian standards for fetal growth (Kramer, M. S., R. W. Platt, S. W. Wen, K. S. Joseph, A. Allen, M Abrahamowicz, B. Blondel, and G. Bréart. 2001. "A new and improved population-based Canadian reference for birth weight for gestational age." *Pediatrics* 108:), which indicates that the birth weight of 2,750 g represents the 10th percentile, with a weight of 3750 g at the 70th percentile. Our intent is to avoid extreme cases of growth retardation (i.e., < 2,200 g). All babies in this study will be born at > 37 weeks gestation to avoid the complication of prematurity and growth restriction. We will recruit two cases for each case (i.e., two infants of normal birth weight for each infant that is small for gestational age).

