The method of recruitment for the MAVAN Study will follow the same procedures as another CIHR-funded follow-up study of the Prematurity Study. The New Mothers Study ([name], PI, [name], [name], [name], and [name] co-investigators) examines the physical and psychological well being of mothers during the first year post-partum with particular attention to mothers of babies born with health problems and mothers of low socio-economic status. The New Mothers Study is in its fourth year. Letters are sent to the mothers about the follow-up to the Prematurity Study with a rejection card and postage paid envelope. Women who do not wish to receive a phone call for the follow-up study simply put the rejection card in the envelope and in the mail. About 2 women per month choose this option. With a 9% prevalence rate of IUGR, we can expect that 126 IUGR babies from the Montreal Prematurity Study will be available as potential participants. Current recruitment rates (~70% participation) suggest that we will obtain a sample of 88 IUGR children and their mothers. Two, normal weight for age babies born on the same or closest day to the IUGR baby will be used as controls with a target of 252. Based on the differential prevalence rates of IUGR among low and high SES mothers, we can expect a sample of 31 low SES mothers and babies in the IUGR group and 57 high SES. Because SES (and associated chronic stressors and depression) may have an adverse effect on child development mediated by postnatal growth delay rather than by IUGR, we will oversample low SES babies who are normal weight for age at birth and consider their postnatal growth as an additional factor predicting cognitive development.

Overview

The measures described here assess the following domains: general development, attention/ impulsivity, social/emotional development, temperament, and basal and stimulated hypothalamic-pituitary-adrenal activity. Methods include measures of parental reports of infant behaviour;

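### The 2004 plan's IUGR n=120 and 120/120 split do not follow from its own recruitment figures, which give 88 IUGR infants (about 76 from the stated pool of 1200) and two controls per case

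*Combined protocol and SAP*

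**What the plan says.** All of this is in the Combined protocol and SAP (2004).

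**III. Methods, Participants**
- Group sizes: "controls, n= 120; 3000-3500 g at birth" and "IUGR, n= 120; 2200-2750 g at birth", so 1:1 and 240 in all.
- Ratio: the same paragraph then asks for "two infants of normal birth weight for each infant that is small for gestational age".
- Source: a prematurity study that will recruit 5000 women, about 4000 of whom will have delivered before this project starts, "leaving a population of 1200 potential subjects". It adds: "Currently, 100 women each month are assessed at 24-26 weeks gestation".
- Yield: "With a 9% prevalence rate of IUGR, we can expect that 126 IUGR babies" will be available from that study. "Current recruitment rates (~70% participation) suggest that we will obtain a sample of 88 IUGR children and their mothers", divided into 31 low-SES and 57 high-SES.
- Controls: two normal-weight babies per IUGR baby "will be used as controls with a target of 252".
- Low-SES normal-weight babies will be oversampled; no number is given.

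**IV. Statistical analysis**
- The power calculation for maternal sensitivity and infant cortisol (r = .30, two-sided alpha .008, power .80) gives 130. Allowing for 13% non-completion it asks for 145 dyads, and concludes that 240 is enough.
- The structural equation modelling (SEM) text expects samples of 210, 292, 366 and 440, depending on the data used.

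**The concern.** The number of growth-restricted infants is a central design quantity, because the main hypothesis is that the postnatal environment determines the effect of fetal adversity. The plan gives no power calculation for the IUGR-control comparison, so the stated group sizes are all a reader has. Those sizes conflict with the expected yield, with the pool and with the ratio, all within one section. A reader cannot tell whether 76, 88 or 120 IUGR infants are planned, or whether the control group is 120, 252 or two per enrolled case. If the 120 is not reached, the contrast could be less precise than the plan suggests.

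**Working it through.** **1. What reproduces.** 126 × 0.70 = 88.2, so 88, and 31 + 57 = 88. The expected yield is therefore a deliberate figure. For the correlation, n = [(z(α/2) + z(power)) / atanh(r)]² + 3 = [(2.652 + 0.842) / 0.3095]² + 3 ≈ 130, as stated.

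**2. What does not: 126 from the pool.** Available = pool × 0.09; enrolled = available × 0.70.

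| Pool | Where it comes from | Available | Enrolled |
|---|---|---|---|
| 1000 | 5000 − about 4000 | 90 | 63 |
| 1200 | stated | 108 | 75.6 (about 76) |
| 1400 | 126 / 0.09; not stated anywhere | 126 | 88 |

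No row gives 120 enrolled. From 126 available, 120 needs 120/126 = 95% participation. From 108 it needs 120/108 = 111%, which is impossible.

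**3. Ratio and controls.** At two controls per enrolled case:
- 88 cases: 176 controls, total 264.
- 76 cases: 152 controls, total 228 (unrounded: 75.6 and 151).

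The stated 252 equals 2 × 126, so it is built on infants available, whereas 88 is infants enrolled. The total of 240 used in the power section comes from 120 + 120.

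**4. Effect on the IUGR-control contrast.** The SE ratio against 120/120 is √(1/n₁ + 1/n₂) / √(2/120), with equal variances. The detectable standardised difference is (1.960 + 0.842) × √(1/n₁ + 1/n₂). This assumes two-sided alpha .05 and 80% power; the plan states neither for this contrast.

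| IUGR / controls | SE ratio | Detectable difference (SD) |
|---|---|---|
| 120 / 120 | 1.00 | 0.36 |
| 88 / 252 | 0.96 | 0.35 |
| 88 / 176 | 1.01 | 0.37 |
| 76 / 152 | 1.09 | 0.39 |

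On the lowest base (1000 women, hence 63/126) the ratio is √((1/63 + 1/126) × 60) = 1.20. That base rests on the rounded 4000, and the plan itself states 1200.

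**5. Attrition.** 130 / 0.87 = 149.4, so 150 dyads. 145 × 0.87 = 126 completers, about 78% power against the stated 80%. The planned 240 leaves 240 × 0.87 = 209 completers, about 96% power. Totals of 228 and 264 leave about 198 and 230, both above 130.

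**The case against.** **120 is a target and 88 an expectation.** This is possible, but the plan names no other source of IUGR infants and no step to close the gap. It would also leave the 1:1 sizes beside the two-controls rule, and 126 beside 108.

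**The inputs are rounded.** Prevalence of 8.5% to 9.5% in 1200 women gives 102 to 114 infants, still not 126, which would need 126/1200 = 10.5%.

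**252 may be meant as an enrolment goal.** This objection stands in part. The plan does not apply the 70% to controls, so calling 252 a pre-participation figure is a reading. The text should say which it is.

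**The practical stakes are low.** This stands. The one formal power calculation concerns two continuous variables and does not depend on the IUGR-control split. The later 72-month Protocol (Analyses) also uses three birth-weight percentile groups crossed with attachment, so 120/120 does not define that analysis.

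Four stronger readings are tempting but not supported:
- *The SEM sizes of 292, 366 and 440 are wrong.* They are not derived, but the low-SES oversample has no number, so no ceiling can be set. For example, 120 IUGR with 240 controls is 360, and 360 × 0.87 = 313 exceeds 292. The plan also calls the SEM secondary.
- *The study is underpowered.* The figures in the working do not show this.
- *120 could be kept by recruiting for longer.* That needs 120 / 0.70 / 0.09, about 1905 women, but the source study stops at 5000 with about 4000 already delivered.
- *The roughly 600 children reported in the 72-month Protocol settle the matter.* They are not broken down by birth-weight group, so they neither show nor exclude an IUGR shortfall.

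**Conclusion.** The point holds as an inconsistency in the 2004 text. The stated 120 IUGR infants are not delivered by the plan's own inputs: 88 are expected (73% of 120), or about 76 (63%) from the stated pool. The 120/120 split contradicts the two-controls rule, 126 does not follow from 1200, and 252 and 88 rest on different bases. Separately, 145 dyads should be 150.

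Severity is minor. If two controls per case are kept, the standard error of the contrast rises about 1% at 88/176 and 9% at 76/152, and the conclusion on maternal sensitivity is unchanged. This rests on the stated 9% and roughly 70%, on equal variances, and on 9% applying to the whole pool. Because eligibility also requires 2200-2750 g and more than 37 weeks, 76 to 88 may be optimistic; the documents give no figure to quantify that.

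**What to change.** Reconcile Participants and Statistical analysis to one chain of figures:
1. State one pool, explaining how 1200 relates to 5000 less about 4000, and restate the expected IUGR number from it: about 76 from 1200, or 88 only if a base of 1400 is documented.
2. Make the control number and total agree with two controls per case (total about 228 or 264, before the low-SES oversample), or drop that rule. Dropping it for 1:1 would cost precision: the SE against 120/120 rises by √(120/88) − 1 = 17% at 88/88, or √(120/76) − 1 = 26% at 76/76.
3. Say whether 252 is before or after participation.
4. Replace 240 in the power section with the reconciled total, and 145 with 150.
5. Give the size of the oversample and show how 292, 366 and 440 arise, or describe them as not derived.

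The cost is text only; hypotheses, measures and analyses stay as they are. The trade-off is that the stated IUGR number becomes less favourable.

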**Maternal Adversity, Vulnerability and Neurodevelopment (MAVAN)
Project**

Investigators:

Principle Investigator: [name]; Co-Investigators: [name], [name], [name], [name], [name], [name], [name], [name], [name], [name], [name], [name], [name], [name], [name], [name].

Project funded August 1, 2004 through a CIHR Strategic Grant (750,000 per year for 5 years)

Research Project

Submitted for Approval by Douglas Hospital REB

February 25th, 2004

I. Introduction.

Objectives: The probability of chronic illness is strongly influenced by environmental conditions prevailing during development (Hertzman 1999). The frequency of heart disease, diabetes, and mental illness is substantially greater amongst those born and raised in poverty, regardless of social class in adulthood. Adversity associated with poverty produces incomplete, dysfunctional families often rife with domestic violence, malnutrition, drug use, child abuse and neglect. Reproduction within this context is associated with maternal stress, increased risks for infection and thus pre-term labour, perinatal deaths, birth insults, poor nutrition for mother and offspring, and serious compromises in the quality of parent-child interactions. These conditions define high-risk families. For the child, these conditions bear the potential to influence the development of physiological systems that regulate metabolism and cardiovascular function, as well as neural processes underlying emotion and cognition. These effects form the basis for vulnerability for illness.

Perhaps the most dramatic illustration of the relation between adversity in early life and the risk for later illness emerges from studies on birth weight, early growth and health in adulthood. Individuals that were small for gestational age, suggesting some degree of intrauterine growth restriction, are at significantly greater risk for type II diabetes, visceral obesity and hypertension (collectively referred to as the metabolic syndrome). The major predictors of fetal growth restriction and pre-term labour, are maternal stress, infections, malnutrition, and tobacco/alcohol consumption. These risk factors are far more prevalent in low socio-economic status (SES) families and, predictably, low SES is a major risk factor for both intrauterine growth retardation (IUGR) and pre-term labour.

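### Nearest-birth-date control selection and unquantified low-SES oversampling are left unreconciled, and no analysis names SES, so the SES comparability of IUGR and control babies is undetermined

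*Combined protocol and SAP*

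**What the plan says.** All of the control-selection text is in the combined protocol and SAP, III. Methods, Participants.

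- Date rule: "Two, normal weight for age babies born on the same or closest day to the IUGR baby will be used as controls". The stated target is 252. SES plays no part in this rule.
- Oversampling: "we will oversample low SES babies who are normal weight for age at birth and consider their postnatal growth as an additional factor". The reason given is that SES "may have an adverse effect on child development mediated by postnatal growth delay rather than by IUGR". No fraction, number or target SES mix is given. The text does not say whether the oversampled babies replace date-selected controls, are chosen by date within SES groups, or are extra.
- Expected IUGR numbers: "With a 9% prevalence rate of IUGR, we can expect that 126 IUGR babies from the Montreal Prematurity Study will be available", and "Current recruitment rates (~70% participation) suggest that we will obtain a sample of 88 IUGR children and their mothers".
- Expected SES mix of the IUGR group: "we can expect a sample of 31 low SES mothers and babies in the IUGR group and 57 high SES". This is derived as follows: "Based on the differential prevalence rates of IUGR among low and high SES mothers". The SES-specific rates are not shown.
- Direction of the relation (I. Introduction, Objectives): "low SES is a major risk factor for both intrauterine growth retardation (IUGR) and pre-term labour".

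Section IV, Statistical analysis, plans regression and ANOVA with interaction tests, multilevel models, and then structural equation models. It names no SES covariate or stratum. In the later 72-month Protocol (Analyses, Hypothesis 1), the model is birth-weight class by attachment category. The only variable named for possible ANCOVAs is sleep quality.

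**The concern.** Suppose the two normal-weight births nearest in date to an IUGR baby are both high SES, and a low-SES normal-weight birth follows a few days later. The date rule takes the first two. The oversampling sentence points to the third. The plan does not say which applies, or whether all three are enrolled.

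This matters because the plan's own background makes SES a confounder. It ties low SES to growth restriction, reports that attention deficit disorder is far more prevalent in low-SES environments, and describes SES effects on cognitive and emotional development acting through parental care. An SES difference between IUGR and control babies would therefore appear partly as an IUGR effect. Because parental care is the hypothesised modifier, SES imbalance could also unbalance the moderator between the groups.

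Adding postnatal growth as a factor does not answer this. The plan presents growth delay as a step on the path from SES to outcome, so modelling it does not equalise SES between the groups.

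**Working it through.** **1. The plan's own figures.**
- 2 x 126 = 252, the stated control target. The date rule accounts for all of it, so no separate oversample is budgeted.
- 126 x 0.70 = 88.2, matching 88.
- 31 + 57 = 88, and 31/88 = 35.2% low SES in the IUGR group.
- 252 x 0.70 = 176.4, matching 2 x 88 = 176. The 252 is therefore a count before participation.

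**2. SES mix under the date rule alone.** Let q = 31/88 = 0.352 and overall IUGR prevalence = 0.09 (both from the plan). Let R be the ratio of IUGR prevalence in low to high SES; it is not in the documents and is assumed. The low-SES share s of all births satisfies (1 - s)/s = R x 57/31. The low-SES share among non-IUGR births is c = (s - 0.09q)/0.91.
- R = 1.5: s = 0.266, c = (0.266 - 0.0317)/0.91 = 0.258.
- R = 2: s = 0.214, c = (0.214 - 0.0317)/0.91 = 0.200.

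Controls would be about 20-26% low SES, against 35.2% in IUGR.

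**3. Bias of the crude difference.** Bias = SES effect x (0.352 - c), with an assumed SES effect of 0.3-0.8 SD, the same in both groups.
- Smallest: 0.3 x (0.352 - 0.258) = 0.03 SD.
- Largest: 0.8 x (0.352 - 0.200) = 0.12 SD.

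If low SES and IUGR both worsen the outcome, this bias is away from the null.

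**4. Wider range, and the effect of oversampling.** If low-SES babies are drawn with odds weight w, the control share is wc/(wc + 1 - c). It equals q when w = [q/(1 - q)]/[c/(1 - c)].

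| Assumed s | Implied R | Control share, date rule | Gap to 35.2% (points) | Equalising w |
|---|---|---|---|---|
| 15% | 3.08 | 13.0% | 22.2 | 3.64 |
| 20% | 2.18 | 18.5% | 16.7 | 2.40 |
| 25% | 1.63 | 24.0% | 11.2 | 1.72 |
| 30% | 1.27 | 29.5% | 5.7 | 1.30 |
| 34% | 1.06 | 33.9% | 1.3 | 1.06 |

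At s = 25%, w = 1.5 gives 32.1% (below the IUGR share) and w = 2 gives 38.7% (above it). The plan fixes neither w nor the resulting mix.

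**5. Numbers for SES-matched selection.** 2 x 31 = 62 low-SES and 2 x 57 = 114 high-SES controls, 176 in all.

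A rough supply check fits a normal curve to the plan's two anchors (2750 g as 10th and 3750 g as 70th percentile), giving mean 3460 g and SD 554 g. About 32.6% of births then fall in 3000-3500 g. With 1200 potential subjects and 70% participation, 0.326 x 1200 x 0.70 = 274 controls. Of these, 274 x 0.200 = 55 to 274 x 0.258 = 71 would be low SES. The need for 62 lies inside that range, so a small shortfall is possible. The estimate is crude: the plan's 126 IUGR babies at 9% imply 1400 births, not 1200.

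**The case against.** **The two sentences can be read together.** Oversampled babies could be additional to the date-selected set, or date selection could be done within SES strata. This stands. A reader might infer that the rules are incompatible, but the documents show only an unspecified procedure.

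**Oversampling may remove the imbalance.** This also stands. A reader might infer that the groups will differ in SES whichever rule is followed. That does not follow: a weight of about 1.1-3.6, depending on the source mix, gives equal shares.

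**The reverse bias.** A reader might go on to suppose that oversampling to 50-60% low SES would reverse the bias. That share needs 88-106 of 176 controls, more than the 55-71 estimated above. On that supply the ceiling is 55/176 = 31% to 71/176 = 40%, so any overshoot of 35% is small.

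**Feasibility of oversampling.** Setting 252 against 274 might suggest that there is no room to oversample. But 252 is before participation and 274 after it. Like with like is 176 against 274, or 252 against 0.326 x 1200 = 391, and both leave room.

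**The size is modest and the crude contrast is not the main target.** The 0.03-0.12 SD lies below one standard error of an 88 v 176 comparison, sqrt(1/88 + 1/176) = 0.13 SD, and rests on assumed inputs. The main hypothesis concerns moderation by postnatal environment, and the power calculation concerns maternal sensitivity and infant cortisol. The Introduction also reports that SES effects vanish once parental care is controlled. These points limit the importance. They do not remove the concern: the bias is systematic and does not shrink with sample size, and no section commits every IUGR-control comparison to a model containing parental care.

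**Oversampling has its own purpose.** The plan offers it to study an SES pathway through postnatal growth, not to balance SES. That is fair, and it means SES balance is addressed nowhere.

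**Recruitment is over.** The 72-month Protocol reports about 600 children enrolled and analyses birth-weight percentile groups. A new selection rule cannot change who was enrolled; an SES term in the models can still be added.

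**Conclusion.** The point holds as a gap in specification with a modest, systematic consequence. The plan does not say how date selection and low-SES oversampling combine, sets no control SES mix, and names no SES term in the analysis.

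Under the date rule alone, controls would be about 20-26% low SES against 35% in IUGR. The crude IUGR-control difference would then be biased by about 0.03-0.12 SD. This assumes a prevalence ratio of 1.5-2, an SES effect of 0.3-0.8 SD, and equal participation across SES groups; none of these is given in the documents. With oversampling, neither the size nor the direction of any remaining imbalance can be determined.

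The documents describe one Montreal source cohort, so they give no support to a picture of different sites following different rules.

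**What to change.** 1. **One selection rule.** For each IUGR baby, take the two normal-weight babies nearest in birth date within the same SES stratum, using the SES definition behind the 31/57 split. That gives about 62 low-SES and 114 high-SES controls for 31 and 57 IUGR babies. It satisfies both sentences: selection is still by date, and the low-SES control share rises from a natural 20-26% to 35%. Accept one control where the low-SES supply runs short.

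2. **SES in the analysis, in any case.** Include SES as a factor in all IUGR-control and birth-weight comparisons, including the interaction models and the 72-month birth-weight by attachment analyses. This remains possible after recruitment is complete.

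The cost is protocol and SAP wording, birth dates matched slightly further apart, and possibly a few incomplete 2:1 sets. The SES data appear to exist already: the plan splits the IUGR group by SES, and the six-month household observations checklist includes items on socio-economic position.
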